There are a limited number of studies reporting treatment duration of Class II correction phase using the CMA. The appliance is more efficient for growing patients, but it is also effective for adults. ¹⁰ The CMA workbook states that Class II correction for adults takes an average of 5 months to complete, while children should achieve Class II correction in an average of 3 months. ¹⁰ All studies reporting duration of Class II correction were performed on adolescent patients or growing patients. One study reported 4.9 months for patients with skeletal Class I and 4.2 months for patients with skeletal Class II, with a combined average of 4.6 months.

¹⁶ Another study reported an average of 4.28 months, a third reported 4.4 months, and a fourth study reported an average of 5.2 months. ^{12,14,15} A fourth study reported 6.3 months for total Class II correction time when using a CMA. ¹³ When measuring combined total treatment time (CMA followed by fixed appliances) one study reported an average combined total treatment time be 32.3 months with a conclusion that the CMA is not an efficient way to treat Class II malocclusions. ¹³ However, a second study reported a total treatment time of 18.2 months (5.2 months for CMA and 13.0 months for the rest of the treatment duration), and a third reported an average combined treatment time of 17.6 months. ^{12,15}

One study measured long-term effects of patients treated with a CMA followed by functional fixed appliance. Results indicated minor changes in molar movement when comparing CBCT measurements taken after removal of the fixed appliance and at a 4-year follow up. However, the inclusion criteria for this study were subjects with a Class I skeletal relationship, and an Angle Class II relationship of at least ½ cusp. The significant changes measured were mesial crown tipping of the maxillary first molars and lingual crown torquing of the mandibular incisors.¹⁸

CMA From the Patient's Perspective

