8.0 Inclusion and Exclusion Criteria*

8.1 Describe the criteria that define who will be **included** in your final study sample.

NOTE: This may be done in bullet point fashion.

Response:

Males and Females

Presenting for comprehensive orthodontic treatment at the Postgraduate orthodontic clinic at the UBSDM

Unilateral or bilateral ½-cusp to full-cusp Class II molar and canine relationship

Growing Patients (~12-17y 11m)

Subjects who do not require extractions as part of treatment mechanics

Mild to moderate crowding

8.2 Describe the criteria that define who will be **excluded** from your final study sample.

NOTE: This may be done in bullet point fashion.

Response:
Patients in mixed dentition
Any missing teeth up to and including permanent first molars
Bilateral molar relationship of less than ½ cusp Class II prior to appliance

8.3 Indicate specifically whether you will include any of the following special populations in your study using the checkboxes below.

NOTE: Members of special populations may not be targeted for enrollment in your study unless you indicate this in your inclusion criteria.

Response:		
	Adults unable to consent	
\boxtimes	Individuals who are not yet adults (infants, children, teenagers)	
	Pregnant women	
	Prisoners	

8.4 Indicate whether you will include non-English speaking individuals in your study. **Provide justification if you will exclude non-English speaking individuals.**

In order to meet one of the primary ethical principles of equitable selection of subjects, non-English speaking individuals may **not** be routinely excluded from research as a matter of convenience.

In cases where the research is of therapeutic intent or is designed to investigate areas that would necessarily require certain populations who may not speak English, the researcher is required to make efforts to recruit and include non-English speaking individuals. However, there are studies in which it would be reasonable to limit subjects to those who speak English. Some examples include pilot studies, small unfunded studies with validated instruments not available in other languages, studies with numerous questionnaires, and some non-therapeutic studies which offer no direct benefit.

Response: We will include non-English speaking individuals in our study

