19.0 Data Management and Analysis*

19.1 Describe the data analysis plan, including any statistical procedures. This section applies to both quantitative and qualitative analysis.

Response:

Intra-examiner reliability will be addressed by randomly selecting 5 lateral cephalograms 2 weeks after initial measurements were performed and having the same operator (AN) repeat the landmarking, superimpositions and measurements. The same operator will also repeat measurements on 5 casts 2 weeks after measurements are conducted for the maxillary first molar and canine rotational measurements. Intra-class correlation coefficients will be calculated in order to determine intra-examiner reliability based on the first and second measurements (P < 0.05).

Statistical analysis will be performed using SPSS. A Shapiro-Wilk test will be run to assess for normality. If the data are normally distributed, independent ttests will be ran to compare means between the two treatment groups. If normality assumptions are not met, a Wilcoxon Rank-Sum test will be used to compare means between the two treatment groups for all measurements.

19.2 If applicable, provide a power analysis.

NOTE: This may not apply to certain types of studies, including chart/records reviews, survey studies, or observational studies. This question is asked to elicit whether the investigator has an adequate sample size to achieve the study objectives and justify a conclusion.

Response:

Sample size estimation: Based on a power of 80% and a significance level of 0.05, it was determined that a sample of size of 16 per treatment group, or a total of 32 participants, would be sufficient in order to have a standardized effect size of 1.02366. These calculations were made based on mean values reported for total treatment time (in months) to achieve Class II correction using a CMA in previous studies. ^{12,14,15,16}

19.3 Describe any procedures that will be used for quality control of collected data.

Response:

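### The primary duration comparison is fixed as an unadjusted two-group test, although the protocol's background links baseline characteristics to correction time and suitable covariates are already collected

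*Protocol*

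**What the plan says.** The primary objective (Protocol, 1.0) is the time in months from bonding until a Class I molar relationship is reached and the appliance is removed.

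On what affects that time, section 4.1 states: "The appliance is more efficient for growing patients, but it is also effective for adults". It then cites a manufacturer's workbook with an average of 5 months in adults, while "children should achieve Class II correction in an average of 3 months". One study is reported with 4.9 months in skeletal Class I and 4.2 months in skeletal Class II patients. The same section says that all studies reporting duration were in adolescent or growing patients.

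Section 8.1 admits growing patients of about 12 to 17 years 11 months, and severity is set as "Unilateral or bilateral ½-cusp to full-cusp Class II molar and canine relationship".

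For the analysis, section 19.1 says that under normality "independent ttests will be ran to compare means between the two treatment groups". Otherwise: "If normality assumptions are not met, a Wilcoxon Rank-Sum test will be used to compare means between the two treatment groups". This covers all measurements, duration included, and no covariate enters either test. Section 19.2 sizes the trial at "16 per treatment group, or a total of 32 participants".

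Section 12.2 collects age, and a cephalometric molar relationship in mm at T0 and T1. Section 21.2 specifies age at T0.

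**The concern.** Treatment stops when a Class I relationship is reached, so a full-cusp case starts further from the endpoint than a half-cusp case. That difference exists before randomisation and has nothing to do with the appliance. The background adds growth status and skeletal class as characteristics that go with duration. The stated test leaves all of this in the error term.

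With 32 subjects, two things are at stake. Any variance that known baseline factors could explain makes the comparison less precise than it need be. An uneven split of such a factor between the arms moves the estimated difference in months, and the stated analysis has no means of correcting for it. If adjustment is not fixed in advance, making it after an imbalance has been seen becomes a discretionary choice.

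**Working it through.** **1. Reproduce the plan's sample size.** Inputs from 19.2: "Based on a power of 80% and a significance level of 0.05", a "standardized effect size of 1.02366", and 16 per arm. Two-sided testing is assumed, since the sidedness is not stated. Two-sample t-test: noncentrality = d × √(n/2) = 1.02366 × √8 = 2.895, with 30 degrees of freedom. Power = 0.800, so the stated N is correct. A one-sided test would need only 12 per arm by the normal approximation, so two-sided is the reading that fits.

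**2. What the documents quantify.**

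| Contrast in 4.1 | Difference | Within eligibility? |
|---|---|---|
| Adults versus children (workbook) | 5 − 3 = 2 months | No, adults are excluded |
| Skeletal Class I versus II (one study) | 4.9 − 4.2 = 0.7 month | Yes, adolescent or growing patients |
| Half- versus full-cusp | not given | – |
| Unilateral versus bilateral | not given | – |

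The 2-month figure is therefore at most an upper bound.

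**3. Share of variance.** The protocol gives no SD in months. Assume a within-stratum SD of 1.5 months and a factor carried by half of the subjects. Share = (shift²/4) / (SD² + shift²/4):

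- 0.7 month: 0.1225 / 2.3725 = 5%
- 1 month (assumed): 0.25 / 2.50 = 10%
- 2 months (upper bound): 1.00 / 3.25 = 31%

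The result depends on the SD. At an SD of 1.0 the three shares are 11%, 20% and 50%; at 2.0 they are 3%, 6% and 20%.

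**4. Power with adjustment.** For the same raw difference, the effective size is d / √(1 − share). With 28 degrees of freedom (two covariates):

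| Share explained | Effective d | Power |
|---|---|---|
| 0% | 1.024 | 0.798 |
| 5% | 1.050 | 0.818 |
| 10% | 1.079 | 0.838 |
| 31% | 1.230 | 0.919 |

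A third term (27 degrees of freedom) lowers each figure by about 0.001. If the covariates explained nothing, the loss would be 0.002.

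**5. Chance imbalance.** Take 32 subjects, 16 of them with the factor, split 16:16 without balancing on it (hypergeometric). A difference of 4 or more carriers between arms has probability 0.289, and of 6 or more 0.076. If each arm is instead treated as an independent sample with 50% carriers, the probabilities are 0.215 and 0.050. Shift in the mean difference = (count difference / 16) × shift:

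- 4 subjects: 0.18, 0.25 or 0.50 month for shifts of 0.7, 1 or 2 months
- 6 subjects: 0.26, 0.38 or 0.75 month

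For scale, the planned detectable difference is 1.02366 × total SD. With total SDs of √2.3725 = 1.54 to √3.25 = 1.80 months, that is about 1.6 to 1.85 months.

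**The case against.** A reader might infer from section 4.1 that maturity shifts correction time by about 2 months in this trial. The documents do not support that. The figure is a manufacturer's contrast of adults with children, and adults cannot enrol. The study means in the same section (4.28 to 6.3 months, all in adolescent or growing patients) are not close to the 3 months quoted for children either.

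A reader might also infer that half- versus full-cusp or one- versus two-sided cases differ in duration by a known amount. No such figure is given, and a longer distance need not mean a proportionally longer time.

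Nor is the planned test wrong. Under randomisation its type I error already allows for chance imbalance, which is not bias, and N reproduces exactly. An imbalance of 4 subjects moves the estimate by well under a third of the detectable difference, so it would rarely decide the result alone. All of this stands.

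It can also be said that covariate adjustment often belongs in a statistical analysis plan, that section 12.1 refers to a randomisation protocol it does not reproduce, and that this is a pilot. That carries less weight for the analysis, because 19.1 does not leave the method open: it names unadjusted tests for all measurements. It does carry weight for randomisation, so the absence of a named stratification factor is not counted as a fault here.

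**Conclusion.** The concern holds as a matter of efficiency and robustness. The background signals that baseline characteristics go with duration, eligibility is broad, and 19.1 fixes a comparison that uses none of them although two suitable covariates are already collected. The unadjusted test remains valid.

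The gain is modest on the documented evidence. The only within-range difference, 0.7 month, corresponds to about 5% of the variance at an assumed SD of 1.5 months and lifts power from 0.80 to about 0.82. It arises from skeletal class, so it indicates scale and does not predict what age and molar relationship would explain. Power of 0.84 rests on an assumed 10% share. Power of 0.92 would need the full adult-versus-child gap to apply to half of the subjects, which is an upper bound. Since adjustment costs almost nothing even if the covariates prove useless (0.798 against 0.800), the change is worth making.

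**What to change.** In section 19.1, pre-specify as the primary duration analysis a linear model of duration on treatment, T0 molar relationship (mm) and age at T0, reporting the adjusted difference in months with its confidence interval. Keep the unadjusted t-test or Wilcoxon comparison as supportive. State how the T0 molar relationship is taken in one-sided cases, since 12.2 lists a single cephalometric value without a side.

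Optionally, for subjects not yet randomised, stratify allocation by unilateral versus bilateral presentation, which is known before bonding. If that is done, include the stratum in the model.

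Cost: one regression model and two of the 30 degrees of freedom, or three with the stratum. No new measurement is needed and treatment is unchanged. Stratification cannot be applied to subjects already randomised. The model must be fixed before the durations are compared by arm.

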5.0 Study Design*

5.1 Describe and explain the study design (e.g. case-control, cross-sectional, ethnographic, experimental, interventional, longitudinal, observational).

Response:

This will be a pilot randomized clinical controlled trial including males and females with a unilateral or bilateral ½ cusp to full cusp Class II molar and canine relationship and mild to moderate crowding. The sample consists of adolescent patients who are receiving comprehensive full fixed appliance orthodontic treatment at the Postgraduate orthodontic clinic at the UBSDM. Subjects will be randomized into one of two treatment groups. Subjects will receive Class II correction prior to orthodontic treatment using either the CMA or an in-office fabricated Class II correction appliance. Lateral cephalometric radiographs and digital models will be taken at: T0 (initial records appointment) and T1(the appointment where the appliance is removed once Class II molar correction has been achieved). Patients in both treatment groups will use the same mandibular anchorage protocol (essix with 2 mm thickness and a button bonded to the buccal surface of the mandibular first molars). Elastic progression for both treatment groups will follow the protocol recommended by the CMA manufacturer (Force 1 Class II elastics (1/4, 6 oz) will be worn for 1 month, and Force 2 Class II elastics (3/16, 8 oz) will be worn for the remainder of Class II correction). Dental and skeletal changes will be measured using lateral cephalometric radiographs taken at T0 and T1, and rotational movements of the maxillary first molar and canine will be assessed using superimposition of the maxillary models taken at T0 and T1 using the e- model Compare 8.1 software by Geodigm. Treatment duration will be calculated (in months) starting on the date the appliance was bonded and ending on the date of appliance removal. Treatment duration and dental and skeletal movements will be compared between the two treatment groups.

6.0 Study Intervention/Investigational Agent

Page 13 of 49

6.1 Describe the study intervention and/or investigational agent (e.g., drug, device) that is being evaluated.

Response:

The CMA is made of a rigid, Nickle free stainless-steel bar that extends from a canine pad to form a ball and socket joint with a molar pad. It is bonded to the labial surfaces of the maxillary canine and maxillary first molar, using composite resin in the same fashion that a bracket would be bonded to a tooth for orthodontic treatment. The goal of the CMA is to allow for a sagittal first approach to achieve Class II molar correction prior to comprehensive orthodontic treatment through distalization of the maxillary buccal segments (maxillary canine and beyond) without the additional vectors of force created when completing Class II correction using continuous orthodontic archwire and brackets, and Class II elastics.⁴

The in-office appliance utilized in our treatment will be fabricated by one operator (AN), and it will consist of a 0.022" slot MBT maxillary second molar mini tube that will be modified to have a tube length of 2 mm, and a 0.018" slot MBT maxillary canine bracket. The appliance will be fabricated using a 3d-printed model of the subject's maxillary arch. The maxillary second molar tube will be cemented on the center of the buccal surface of the maxillary first molar of the 3D-printed model. A 0.016x0.022" stainless steel wire with a bayonet bend positioned mesial to the maxillary first molar and a curve extending from the maxillary first molar to the maxillary canine will be placed, and it will guide the placement of the maxillary canine bracket, so that the stainless-steel wire can sit passively in both the molar tube and canine bracket slot. Once the maxillary canine bracket has been bonded, a pre-cut, closed-coil stainless-steel spring that spans from the mesial opening of the first molar tube to the distal wing of the canine bracket will be placed, and the wire will then be steel tied to the maxillary canine bracket, and then it will be cut and cinched mesial to the maxillary canine bracket. The wire will also be cinched 2-3 mm distal to the maxillary molar tube, to ensure that once the wire is placed, the molar still will maintain the ability to rotate, if needed. The operator will then remove the appliance in one piece from the model and will sand blast any excess resin off the bracket and molar tube. The same operator (AN) will instruct the treating resident on how to place the appliance: the molar tube will be placed in the center of the buccal surface of the maxillary first molar and will be light cured. The canine bracket will then be placed so that the bayonet bend is in contact with the mesial surface of the maxillary first molar tube and the wire is passive. The same anchorage protocol and elastic regimen will be utilized in the in-office Class II corrector group.

Both the CMA and the in office fabricated appliance will be utilized for Class II correction prior to comprehensive orthodontic treatment, and mandibular anchorage is necessary for both appliances. In our study we will be utilizing one of the CMA manufacturer's recommended mandibular anchorage protocols: a fabricated 2 mm essix retainer. An orthodontic button will be bonded to the buccal surface of the mandibular first molar on the affected side to provide mandibular anchorage for elastic use during Class II correction. Elastic

progression will follow the protocol recommended by the CMA manufacturer (Force 1 Class II elastics (1/4, 6 oz) will be worn for 1 month, and Force 2 Class II elastics (3/16, 8 oz) will be worn for the remainder of Class II correction) until a Class I molar relationship has been achieved.

- 1.1 Drug/Device Handling: If the research involves drugs or device, describe your plans to store, handle, and administer those drugs or devices so that they will be used only on subjects and be used only by authorized investigators.
- If the control of the drugs or devices used in this protocol will be accomplished by following an established, approved organizational SOP (e.g., Research Pharmacy SOP for the Control of Investigational Drugs, etc.), please reference that SOP in this section.

Response:

N/A

- 6.2 If the drug is investigational (has an IND) or the device has an IDE or a claim of abbreviated IDE (non-significant risk device), include the following information:
 - *Identify the holder of the IND/IDE/Abbreviated IDE.*
 - Explain procedures followed to comply with sponsor requirements for FDA regulated research for the following:

		Applicable to:	
FDA Regulation	IND Studies	IDE studies	Abbreviated IDE studies
21 CFR 11	X	X	
21 CFR 54	X	X	
21 CFR 210	X		
21 CFR 211	X		
21 CFR 312	X		
21 CFR 812		X	X
21 CFR 820		X	

Response:

N/A

7.0 Local Number of Subjects

7.1 Indicate the total number of subjects that will be enrolled or records that will be reviewed locally.

Response: 16 subjects per treatment group, (N = 32)

Page 15 of 49

7.2 If applicable, indicate how many subjects you expect to screen to reach your target sample (i.e. your screen failure rate).

Response:

Approximately 720 to 840 subjects

7.3 Justify the feasibility of recruiting the proposed number of eligible subjects within the anticipated recruitment period. For example, how many potential subjects do you have access to? What percentage of those potential subjects do you need to recruit?

Response:

Our study will be screening the entire prospective patient pool in the University at Buffalo School of Dental Medicine's orthodontic clinic for the first- and second-year residents. One operator (AN) will instruct all residents completing patient screenings and acceptance of patients on criteria necessary to become a subject in the current study. The same operator will also evaluate all eligible subjects and see if they meet all inclusion criteria and proceed to inform the subjects of their eligibility and purpose of the study. Each resident can screen approximately 60-70 patients over 6 months. If we utilize the patient pools of twelve residents, we can approximate 720 to 840 patients total. Not all patients will meet the inclusion criteria required for the study, and other treatment modalities of Class II correction are available as a part of comprehensive orthodontic treatment. Therefore, not all Class II patients who meet the criteria will be using the CMA or in-office appliance for Class II correction as a part of their comprehensive orthodontic treatment.

8.0 Inclusion and Exclusion Criteria*

8.1 Describe the criteria that define who will be **included** in your final study sample.

NOTE: This may be done in bullet point fashion.

Response:

Males and Females

Presenting for comprehensive orthodontic treatment at the Postgraduate orthodontic clinic at the UBSDM

Unilateral or bilateral ½-cusp to full-cusp Class II molar and canine relationship

Growing Patients (~12-17y 11m)

Subjects who do not require extractions as part of treatment mechanics

Mild to moderate crowding

8.2 Describe the criteria that define who will be **excluded** from your final study sample.

NOTE: This may be done in bullet point fashion.

Response:
Patients in mixed dentition
Any missing teeth up to and including permanent first molars
Bilateral molar relationship of less than ½ cusp Class II prior to appliance

8.3 Indicate specifically whether you will include any of the following special populations in your study using the checkboxes below.

NOTE: Members of special populations may not be targeted for enrollment in your study unless you indicate this in your inclusion criteria.

Response:		
	Adults unable to consent	
\boxtimes	Individuals who are not yet adults (infants, children, teenagers)	
	Pregnant women	
	Prisoners	

8.4 Indicate whether you will include non-English speaking individuals in your study. **Provide justification if you will exclude non-English speaking individuals.**

In order to meet one of the primary ethical principles of equitable selection of subjects, non-English speaking individuals may **not** be routinely excluded from research as a matter of convenience.

In cases where the research is of therapeutic intent or is designed to investigate areas that would necessarily require certain populations who may not speak English, the researcher is required to make efforts to recruit and include non-English speaking individuals. However, there are studies in which it would be reasonable to limit subjects to those who speak English. Some examples include pilot studies, small unfunded studies with validated instruments not available in other languages, studies with numerous questionnaires, and some non-therapeutic studies which offer no direct benefit.

Response: We will include non-English speaking individuals in our study

